2) The pooled standard deviation for the changes in hemoglobin level was 15 g/L.
3) Non-inferiority margin is 5 g/L.
4) The significance level (two-sided, in accordance with FDA recommendations) is 95%, which corresponds to the type I one-sided error 0.05.
5) Power of the study is 80%, which corresponds to the type II error 0.20.
6) Statistical hypotheses – evidence of a non-inferior efficacy:
H0: $\mu_{A} - \mu_{B} \le 5.0$ H1: $\mu_{A} - \mu_{B} > 5.0$
7) The ratio between the study and control group sizes is 1:1
8) Interim analysis will be performed at 70% of the total sample size

 
9) O'Brien-Fleming alpha-spending function will be used with 80% power for efficacy boundary that will correspond to the following critical values for t-test: 2,628 for interim analysis (corresponds to p=0,005) and 1,976 for final analysis (corresponds to p=0,0245);
 

Calculation was performed using the clinfun package of Microsoft R Open software (available at https://mran.microsoft.com – Microsoft R Application network), that uses the group sequential design approach for the calculation of fixed sample sizes for the interim and final analysis.
According to the output from the clinfun package, 143 subjects per group (286 subjects in total) should complete the study in order to

confirm non-inferiority. 200 (100 per group) subjects should have evaluable data to perform interim analysis. Taking 15% withdrawal rate into account, one need to randomize 336 subjects (168 subjects per group). Taking 30% screening failure rate, up to 480 subjects should be screened to achieve target randomization.
should be serected to achieve target randomization.

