#### 9.1.2 Analysis of the primary efficacy endpoint

#### Primary efficacy endpoint:

• Changes in blood haemoglobin level (g/L) after 12-weeks of iron-deficiency anaemia treatment (during the final visit), as compared with the baseline value (the screening visit) between the study groups.

Analysis of covariance (ANCOVA) will be used as the main method of assessment of the primary endpoint, with baseline haemoglobin value being a covariate and four fixed factors (treatment group, gender, weight and baseline Hb level (80–94 g/L vs 95–110 g/L). Unrestricted least significant differences (LSD) method will be applied to the ANCOVA results with the calculation of least-square (LS) means with 95% CI for LS means for the difference between the study groups. Non-inferiority will be confirmed if the upper limit of the two-sided 95% confidence interval for LS mean will not exceed the pre-defined non-inferiority margin of 5 g/L.

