8.1. Primary endpoint analysis

• Changes in hemoglobin level (g/L) after 12 weeks of iron deficiency therapy (at the final visit) as compared to baseline (determined at the screening visit) in the study groups.

STATISTICAL ANALYSIS PLAN

The covariance analysis (ANCOVA) will be used as the main method for assessing the primary endpoint, with the baseline blood hemoglobin level as a covariate, and four fixed factors (treatment group, sex, weight, and baseline hemoglobin level (80-94 g/L vs. 95-110 g/L). The method of unrestricted least significant differences (LSD) will be applied to ANCOVA results with LS mean values from 95% CI for mean values calculated by the method of least squares for differences between the studied groups. Due to the obvious dependence of the covariates and the base hemoglobin factor (80-94 g/L compared to 95-110 g/L), a linear model containing the term of interaction between these variables will be used.

Non-inferiority will be confirmed if the upper bound of a two-sided confidence interval for the mean value calculated by the method of least squares does not exceed the predetermined non-inferiority margin of 5 g/L. The CI percentage will be determined by the moment of the analysis (interim/final) in accordance with clause 2.3 of the Statistical Analysis Plan.

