Appendix 1. Table layouts

PRIMARY ENDPOINT

Parameter	Coef.	Standard error	t -value	p -value	С	2I
Constant (intercept)						
Group R versus Group T						
Gender M versus F						
Weight						
Base hemoglobin factor (80–94 g/L compared to 95–110 g/L)						
Hemoglobin level at screening						
Interactions						

SECONDARY ENDPOINTS

Table 1. Hemoglobin, frequency analysis of the treatment efficacy after 12 weeks

Hemoglobin (g/L)					
Group	Parameter	Value			
	Total observations				
$R - Maltofer^{\mathbb{R}}$	Responders, n				
	Responders, %				
	95% CI				
	Total observations				
T – Ferrum Lek®	Responders, n				
	Responders, %				
	95% CI				
Group comparison	Pearson's chi-square test, p-value				

Table 2. Results of analysis of variance

Coefficients	Evaluation	Standard error	t-value	p-value
(Intercept)				
V1_CB_LBORRES_HB				
(Hemoglohin level at screening)				
Group T – Ferrum Lek [®]				
(Test to reference group factor)				

Table 3. Hemoglobin, absolute values, g/L

Hemoglobin (g/L)						
Group	Parameter	Screening	Week 4	Week 8	Week 12	
	Number of observations					
	Number of missing values					
	Mean value					
R – Maltofer®	95% CI					
	Standard deviation					
	Median					
	Minimum value					
	Maximum value					

	1st quartile		
	3rd quartile		
	Interquartile range		
	p-value (Shapiro–Wilk test)		
	Number of observations		
	Number of missing values		
	Mean value		
	95% CI		
	Standard deviation		
	Median		
T – Ferrum Lek [®]	Minimum value		
	Maximum value		
	1st quartile		
	3rd quartile		
	Interquartile range		
	p-value (Shapiro–Wilk test)		
Group	Criterion		
comparison	p-value		

SOP-05-02_RF01 Statistical Analysis Plan_01APR2020_3.0

Table 4. Hemoglobin, changes, g/L

Hemoglobin (g/L)						
Group	Parameter	Week 4 – Screening	Week 8 – Screening	Week 12 – Screening		
	Number of observations					
	Number of missing values					
	Mean value					
	95% CI					
	Standard deviation					
	Median					
R – Maltofer®	Minimum value					
	Maximum value					
	1st quartile					
	3rd quartile					
	Interquartile range					
	p-value (Shapiro–Wilk test)					
	Number of observations					
	Number of missing values					
	Mean value					
T − Ferrum Lek®	95% CI					
	Standard deviation					
	Median					
	Minimum value					

STATISTICAL ANALYSIS PLAN

	Maximum value		
	1st quartile		
	3rd quartile		
	Interquartile range		
	p-value (Shapiro–Wilk test)		
Group comparison	Criterion		
	p-value		

Table 5. Blood serum iron, absolute values, μ mol/L

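### The printed hypotheses are not non-inferiority hypotheses and contradict the confidence-limit rule, which does not say which product is subtracted from which

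*Protocol*

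**What the plan says.** The primary endpoint is the change in haemoglobin from screening to week 12, and the main objective is non-inferiority of Ferrum Lek to Maltofer.

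- **Hypotheses.** Item 6 of the sample-size justification in the protocol synopsis, presented as the non-inferiority hypotheses, gives the null as "H0: $\mu_{A} - \mu_{B} \le 5.0" and the alternative as "H1: $\mu_{A} - \mu_{B} > 5.0". A and B are not defined there or anywhere else in the two documents.
- **Decision rule, protocol.** The Synopsis and section 9.1.2 both say: "Non-inferiority will be confirmed if the upper limit of the two-sided 95% confidence interval for LS mean will not exceed the pre-defined non-inferiority margin", with a margin of 5 g/L. The quantity estimated is described as "least-square (LS) means with 95% CI for LS means for the difference between the study groups", with no order of subtraction.
- **Decision rule, SAP.** Section 8.1 keeps the upper-limit form, "Non-inferiority will be confirmed if the upper bound of a two-sided confidence interval", and makes the confidence level depend on the look: "The CI percentage will be determined by the moment of the analysis (interim/final". It gives no order either.
- **Only pointer to direction.** The primary-endpoint table shell in SAP Appendix 1 has a row labelled "Group R versus Group T". Elsewhere in that appendix R is Maltofer and T is Ferrum Lek.

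**The concern.** A non-inferiority test on a higher-is-better endpoint needs an alternative saying that the test product is not worse than the reference by the margin or more. The printed alternative does not say this under either labelling. It also points the opposite way from the rule: an upper limit at or below 5 g/L is evidence against a difference above 5 g/L, yet the rule counts it as success.

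The rule has its own gap. An upper limit compared with +5 tests non-inferiority only when the difference is reference minus test. Taken as test minus reference, it shows only that Ferrum Lek is not much better than Maltofer, which a clearly worse product would pass easily.

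This is the trial's only confirmatory test, since all secondary analyses are declared exploratory. The study is open-label, and the sponsor may stop it at the interim on this result. The direction should therefore be fixed in the rule before any data are examined.

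**Working it through.** **Inputs** (synopsis sample-size justification, repeated in Protocol 9.3 and SAP 2.3): margin 5 g/L; SD 15 g/L; assumed true difference 0; power 80%; 143 completers per arm; interim at 100 per arm; critical values 2.628 (interim) and 1.976 (final).

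**1. The plan's own sample size.** Fixed design, one-sided 0.025:

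n = 2 × 15² × (1.960 + 0.842)² / 5² = 141.3 per arm, so 142.

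A two-look calculation with the stated boundaries at 70% information needs 142.1 per arm for 80% power. Both agree with the stated 143. The design was therefore sized as an ordinary non-inferiority trial with overall one-sided error 0.025.

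**2. The hypotheses as printed.**

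| Labelling | Printed alternative (μA − μB > 5) means | Non-inferiority? |
|---|---|---|
| A = Ferrum Lek, B = Maltofer | Ferrum Lek better by more than 5 g/L | No: superiority by a margin |
| A = Maltofer, B = Ferrum Lek | Ferrum Lek worse by more than 5 g/L | No: null and alternative are transposed |

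The standard error at 143 per arm is 15 × √(2/143) = 1.774 g/L. At the planned difference of 0, the chance of rejecting the printed null at one-sided 0.025 is 1 − Φ(1.96 + 5/1.774) ≈ 9 × 10⁻⁷, against a planned 80%. For 80% power the true difference would have to be 5 + 2.80 × 1.774 = 9.97 g/L.

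**3. The decision rule in each order.** Let d be the true shortfall of Ferrum Lek in g/L.

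- Interim: SE = 15 × √(2/100) = 2.121; half-width = 2.628 × 2.121 = 5.575.
- Final: half-width = 1.976 × 1.774 = 3.505.
- The two looks are correlated √(100/143).

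*Maltofer − Ferrum Lek.* Final-look pass probability = Φ((5 − 3.505 − d)/1.774).
- d = 0: 80.0% at the final look, 80.2% over both looks.
- d = 5: 2.4% at the final look, 2.50% over both looks.

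*Ferrum Lek − Maltofer.* Final-look pass probability = Φ((5 − 3.505 + d)/1.774).
- d = 5 (5 g/L worse): 99.99% at the final look; at the interim Φ((5 − 5.575 + 5)/2.121) = 98.2%; 99.99% over both looks.
- d = −5 (5 g/L better): 2.4% at the final look taken alone.

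**4. Sensitivity to the interim size.** Protocol 9.2 puts the interim at 120 per arm or more, whereas the sample-size text and SAP section 11 say 100. With 120 per arm, two-look error in the valid order is 2.43%, and the interim pass rate for a product 5 g/L worse in the reverse order is 99.4%. The conclusion does not change.

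**The case against.** The strongest reply is that the intent is plain and the operative rule works. Item 6 is presented as non-inferiority, the objectives and the margin use the same term, the assumed difference is zero, and 143 per arm reproduces only as a non-inferiority design. No analysis step uses the printed hypotheses; the decision rests on the confidence limit. The SAP primary shell gives reference versus test, the one order in which the rule is valid, so the 99.99% figure needs an analyst to depart from that shell. On this view the fault is a misprint.

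Much of this is right. The intent is clear, the sample size is sound, and the reverse-order figure is conditional. Three things remain. The printed pair is still wrong under both labellings. A coefficient-table row label is weak authority for the direction of the primary contrast, and the secondary haemoglobin model in SAP Appendix 1, Table 2, labels its group term the other way, as Ferrum Lek relative to the reference. Nor does the rule's own text settle the matter in either document.

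A minus sign before 5.0 could have been lost in text extraction. The sign between the two means survives, however, and 5.0 is unsigned in both synopsis lines and in the one line visible in SAP 2.3. Even with −5.0 and A as Ferrum Lek, the matching rule for A − B would be a lower limit above −5, not an upper limit. The hypothesis lines of Protocol 9.3, and the rest of the pair in SAP 2.3, are not visible in the text reviewed. Nothing is inferred from their absence, and the error is shown for the synopsis.

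**Conclusion.** The concern holds and must be fixed. The synopsis hypotheses are not non-inferiority hypotheses under any assignment of A and B, and success under the decision rule lies inside the printed null. The rule itself is a valid test for Maltofer minus Ferrum Lek, with 2.5% overall one-sided error and 80.2% power, but neither statement of it gives that order. The consequence of the reverse order would be severe: a 99.99% pass rate for a product 5 g/L worse. That arises only if that order were actually used. These figures assume SD 15 g/L, normally distributed estimates, looks at 100 and 143 per arm, and the stated boundaries at each look. The sample size is unaffected.

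**What to change.** Define the two groups by product name and place the contrast next to the rule. Either form will do:

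- **(a)** Δ = Maltofer − Ferrum Lek; H0: Δ ≥ 5; H1: Δ < 5; non-inferior if the upper limit of the look-specific confidence interval is below 5 g/L.
- **(b)** Δ = Ferrum Lek − Maltofer; H0: Δ ≤ −5; H1: Δ > −5; non-inferior if the lower limit is above −5 g/L.

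The two are equivalent. Option (a) keeps the existing upper-limit rule. Put one identical statement in the synopsis, Protocol 9.1.2 and 9.3, SAP 2.3 and 8.1, and the primary table shell, and name the products in the shell's group row.

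The cost is wording in the protocol and SAP. No extra patients or data are needed, and the sample size stays at 143 completers per arm.

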# **1** General information

## 1.1 Protocol name, Protocol ID, and date:

**Name**: A multicenter, open-label, randomized, active-controlled study to evaluate the efficacy and safety of Ferrum Lek® (iron (III) hydroxide polymaltosate), 100 mg chewable tablets (Lek d.d., Slovenia), as compared with Maltofer® (iron (III) hydroxide polymaltosate), 100 mg chewable tablets (Vifor S.A., Switzerland), in subjects with mild and moderate iron deficiency anemia.

ID: TE\_005\_FER\_CHT Protocol version: 2.0 Date: March 20, 2019

# 1.6 Clinical laboratories and other organizations engaged in the study

# 2 Study rationale

## 2.1 Study drugs

## 2.1.1 Study drug: Ferrum Lek®

Trade name: Ferrum Lek®

**International non-proprietary name or generic name:** iron [III] hydroxide polymaltosate. **Chemical name:** iron [III] hydroxide polymaltosate

**Dosage Form:** chewable tablets

#### **Composition:**

1 chewable tablet contains:

Active substance: iron (III) hydroxide polymaltosate 400 mg (equivalent to 100 mg of iron).

Excipients: macrogol 6000 - 37.0 mg; aspartame - 1.5 mg; chocolate flavoring - 0.6 mg; talc - 21.0 mg; dextrates to 730.0 mg.

#### **Appearance:**

Dark brown, round, flat tablets with light brown impregnations and a bevel edge.

Pharmacotherapeutic group: iron drug.

ATC code: B03AB05.

#### Pharmacodynamic properties

#### **Pharmacodynamics**

Polynuclear iron (III) hydroxide is surrounded by a number of covalently bound polymaltose molecules from the outside in iron (III) hydroxide polymaltosate, which gives a total average molecular weight of about 50 kDa.

The polynuclear iron (III) hydroxide polymaltosate core has a structure similar to that of the core of the physiological iron storage protein ferritin. Iron (III) hydroxide polymaltosate is stable and under physiological conditions does not emit a large number of iron ions. Due to its size, iron (III) hydroxide polymaltosate diffusion degree through the mucosa is approximately 40 times less than that of the iron (II) hexahydrate complex. Iron from iron (III) hydroxide polymaltosate is actively absorbed in the intestine.

The efficacy of iron (III) hydroxide polymaltosate for normalizing the hemoglobin content and iron pool replenishment was demonstrated in numerous randomized controlled clinical studies using placebo or an active comparator in adults and children with different iron pool status.

#### Pharmacokinetics

#### Absorption

Iron from iron (III) hydroxide polymaltosate is absorbed in accordance with the controlled mechanism. The increase in serum iron content after the drug administration does not correlate with total iron absorption, measured as incorporation into hemoglobin (Hb). Studies with a labeled radioisotope of iron (III) hydroxide polymaltosate revealed a strong correlation between the inclusion of iron in erythrocytes and the iron content throughout the body. The maximum activity of iron absorption from iron (III) hydroxide polymaltosate occurs in the duodenum and small intestine. As in case of other oral iron drugs, the relative absorption of iron from iron (III) hydroxide polymaltosate defined as incorporation into hemoglobin, decreases with increasing doses of iron. In addition, a correlation was observed between the degree of iron deficiency (in particular serum ferritin concentration) and the relative amount of absorbed iron (i.e., the greater the iron deficiency, the better the relative absorption). In subjects with anemia, absorption of iron from iron (III) hydroxide polymaltosate, in contrast to iron salts, increased in the presence of food.

#### Distribution

Distribution of iron from iron (III) hydroxide polymaltosate after absorption was studied in a study using the technique of double isotopes (Fe and Fe).

#### Biotransformation

The absorbed iron binds to transferrin and is used to synthesize hemoglobin in the bone marrow or is stored, mainly in the liver, where it binds to ferritin.

#### Excretion

Non-absorbed iron is excreted by the intestine (with feces).

#### Therapeutic indications

- treatment of latent iron deficiency (iron deficiency without anemia);
- treatment of symptomatic iron deficiency anemia;
- increased need for iron during pregnancy and lactation, blood donation, intensive growth, vegetarians and the elderly.

#### Contraindications

- iron overload (e.g., hemosiderosis, hemochromatosis);
- impairment of iron utilization (e.g., lead anemia, sideroachrestic anemia, thalassemia);
- anemia other than iron deficiency anemia (e.g., haemolytic anemia, megaloplastic anemia due to vitamin B12 deficiency);
- children under 12 years old (due to the need to prescribe small doses in this age group it is recommended to use Ferrum Lek® syrup 10 mg/ml).

#### Administration during pregnancy and lactation

#### Pregnancy

Until now, there have been no reports of serious adverse reactions after oral administration of iron (III) hydroxide polymaltosate at therapeutic doses for the treatment of anemia during pregnancy. The data obtained from animal studies showed no danger to the fetus or the mother. There is no clinical data on the use of Ferrum Lek® in the first trimester of pregnancy.

The studies conducted in pregnant women after the end of the first trimester of pregnancy revealed no adverse effects of iron (III) hydroxide polymaltosate in mothers and/or newborns. Consequently, adverse effect on the fetus is unlikely following the administration of iron (III) hydroxide polymaltosate.

#### *Lactation*

Woman breast milk contains iron bound to lactoferrin. The amount of iron that passes from iron (III) hydroxide polymaltosate to breast milk is unknown. It is unlikely that the administration of iron (III) hydroxide polymaltosate in lactating women can lead to adverse effects in the child. As a precaution to women of childbearing age and women during pregnancy and lactation, Ferrum Lek® should be administered only after consultation with the doctor. The benefit/risk ratio should be evaluated.

#### Posology and method of administration

Oral dosage form.

The daily dose can be divided into several doses or taken at a time. Ferrum Lek® should be administered during or immediately after meals. Ferrum Lek®, 100 mg chewable tablets, can be chewed or swallowed whole.

The daily dose of the drug depends on the degree of iron deficiency (see table of daily doses).

#### Table of daily doses

Patient populations	Treatment of iron deficiency anemia	Treatment of iron deficiency without anemia	Increased iron requirement
Children older than 12 years, adults and lactating women	1–3 chewable tablets (100–300 mg of iron)	1 chewable tablet (50–100 mg of iron)	
Pregnant women	2–3 chewable tablets (200–300 mg of iron)	1 chewable tablet (100 mg of iron)	1 chewable tablet (100 mg of iron)

Treatment of iron deficiency anemia in children older than 12 years and adults

100 to 300 mg of iron (1-3 tablets) per day for 3–5 months until the normal hemoglobin (Hb) level is reached. After this, treatment should be continued for several weeks at the dose described for iron deficiency without anemia in order to replenish iron stores.

*Treatment of iron deficiency anemia during pregnancy* 

200 to 300 mg of iron (2–3 tablets) per day until the normal hemoglobin (Hb) level is reached. After this, treatment should be continued at least until the end of pregnancy at a dose described for iron deficiency without anemia in order to replenish iron stores and meet the increased requirements for iron due to pregnancy.

Treatment and prevention of iron deficiency without anemia in children older than 12 years and adults

100 mg (1 tablet) per day for 1–2 months.

Paediatric use

Ferrum Lek® 100 mg chewable tablets are contraindicated for children under 12 years old.

#### Side effects

Ferrum Lek® is generally well tolerated. Side effects are mainly mild and transient.

Side effects are mainly mild and transient. According to the World Health Organization (WHO), adverse reactions are classified depending on their incidence as follows: very common (> 1/100), common (> 1/100, < 1/100), uncommon (> 1/1,000, < 1/100), rare (> 1/10,000, < 1/1,000), very rare (< 1/10,000), not known (cannot be estimated using the available data).

Nervous system disorders

uncommon: headache.

Gastrointestinal disorders

*very common:* feces discolored (in 23% of patients, this is a known adverse reaction to iron drugs); *common:* diarrhea, nausea, indigestion;

*uncommon*: vomiting, constipation, abdominal pain, discoloration of tooth enamel (in 0.6% of patients, this is a known adverse reaction to iron drugs);

Skin and subcutaneous tissue disorders

uncommon: rash, including exanthema, itching.

#### Overdose

In case of an overdose of Ferrum Lek®, iron overload or intoxication is unlikely due to the low toxicity of iron (III) hydroxide polymaltosate and controlled iron uptake. No cases of fatal unintentional poisoning were reported.

#### Interaction with other medicinal products

Interactions of iron (III) hydroxide polymaltosate with tetracycline or aluminum hydroxide have been studied. No significant decrease in tetracycline absorption has been observed. Plasma concentrations of tetracycline did not drop below the effective level. Absorption of iron from iron (III) hydroxide polymaltosate did not decrease under the influence of aluminum hydroxide or tetracycline. Thus, concomitant administration of iron (III) hydroxide polymaltosate with tetracycline and other phenolic compounds, as well as aluminum hydroxide, is allowed. The studies in rats using tetracycline, aluminum hydroxide, acetylsalicylic acid, sulfasalazine, calcium carbonate, calcium acetate and calcium phosphate in combination with vitamin D3, bromazepam, magnesium aspartate, D-penicillamine, methyldopa, paracetamol and auranofin revealed no interactions with iron (III) hydroxide polymaltosate.

No interaction of iron (III) hydroxide polymaltosate with food components such as phytic acid, oxalic acid, tannin, sodium alginate, choline and choline salts, vitamin A, vitamin D3, and vitamin E, soybean oil and soybean flour was observed either. These results indicate that iron (III) hydroxide polymaltosate can be administered during or immediately after meals.

The administration of the drug does not affect the results of the detection of hidden blood (with a selective determination of hemoglobin), therefore, treatment interruption is not necessary.

Concomitant use of parenteral and oral iron drugs should be avoided, since the absorption of iron taken orally slows down.

